## Research Question and Aims

### Aims, purpose, or objectives:

The brachial plexus and peripheral nerves are susceptible to injury during robotic genitourinary surgery. SSEPs are commonly used to detect pending injury to peripheral nerves. The purpose of the present study is to use SSEP monitoring to determine the incidence and potential causes of significant changes in SSEP waveforms and correlate these changes with neurologic status of the brachial plexus after robotic surgery.

### Background:

The EPAD is a Somatosensory evoked potential (SSEP) device intended for use in monitoring a patient's neurological status by recording somatosensory evoked potentials (SSEP) or assessing the neuromuscular junction (NMJ). The EPAD provides information that enables the clinician to detect changes in nerve response waveform amplitude and latency, which may indicate positioning effect nerve injury. The EPAD also provides information that enables the clinician to monitor the depth of neuromuscular block intraoperatively and during recovery. With this information the clinician can take appropriate interventions that will help prevent or ameliorate peripheral nerve injury or post-operative residual paralysis.

The target population for the EPAD includes patients who may benefit from monitoring neurologic responses using somatosensory evoked response stimulation or neuromuscular junction testing. In particular, EPAD is targeted for patients who may be at risk for limb Positioning Effect (PE). PE refers to peripheral nerve impingement related to patient positioning during surgery or prolonged sedation, which may result in numbness, tingling or paralysis.

## Study Design and Methods

### Methods:

Patients scheduled for genitourinary surgery are often at risk for developing nerve injuries due to intraoperative positioning. The anesthesiologists assigned to the case will notify study team members if EPAD system will be used intraoperatively. The study team members will approach the prospective participants to obtain permission to record data for the study purposes. A verbal consent will be obtained.

The EPAD system (manufactured by SafeOP Surgical Inc., Hunt Valley MD) consists of the EPAD Control box, tablet computer, stimulation and acquisition cables, and stimulation and acquisition surface electrodes. █

The EPAD is small and light and the control box, that communicates with the tablet computer through Bluetooth or USB can be mounted to the OR bed rail.

The computer employs a proprietary algorithm that detects changes in evoked response amplitude and latency and alerts the user to check the waveform view for artifact or potential limb positioning effect. A built-in cautery detection circuit that suspends waveform averaging in the presence of high frequency interference prevents contamination of waveforms.

The EPAD software application is preloaded onto the EPAD tablet touchscreen computer. The application serves as the user interface for the EPAD Control box to input patient and procedure information, adjust stimulus and acquisition parameters, control stimulus delivery, display acquired data, and deliver messages and alerts to the clinician. The clinician is able to insert time locked comments throughout the case indicating any interventions or events. At the end of the procedure the tablet features a report generator that summarizes all data acquisition parameters and waveforms with corresponding measurement values. In the report there is a section for comments and interpretation of results by the user with the final report being available to be printed or exported electronically.

Electrode cables are provided for both stimulation and acquisition and are color coded for correct connection to the EPAD Control box. The stimulator cable connectors are also uniquely keyed to assure correct connection to the Control box. Labeled tabs on each cable indicate the locations for appropriate electrode connections.

Eight surface electrodes are applied to the patient for full patient monitoring. The EPAD Electrodes are wet gel electrodes designed to minimize the amount of skin preparation required. The electrodes are single-use, disposable, and biocompatible for use on intact skin and can be expected to perform as intended for up to 24 hours.

## **EPAD Setup**

- Surface electrodes will be used for both recording and stimulation.
- Bilateral Median and Ulnar Nerves will be stimulated at the wrist.
- Recording electrodes are placed on the cervical spine at C5 with the reference electrode placed on the forehead.
- A dual electrode patch is placed over the dorsum of the right hand with the recording electrode placed over the muscle belly of the first dorsal interosseous muscle for recording of the Train of Four.
- The stimulation frequency is 4.7 Hz with a 300 microsecond pulse set at 50 mA.
- Baselines are automatically established at the beginning of the case and the amplitude and latency of the waveforms measured. Establishment of the baselines is indicated in green shading of the arms on a pictogram. Adjacent to the pictogram are the measured values shown in blue for the baseline and in green for the penultimate waveform.
- A decrease of 50% in amplitude and/or an increase of 10% of the latency of one of the potentials as compared to baseline will trigger an alert, indicated by the limb turning yellow and an audio alarm.
- Continuous monitoring will be performed throughout the surgery.

## **Data collection:**

- Patient demographics: age, sex, weight, height
- Medical history (hypertension, diabetes mellitus, history of smoking)
- Patient positioning intraoperatively (hand, arm, and head position)
- Intraoperative time of positioning in extreme Trendelenburg and or lithotomy position.

- Intraoperative time of resumption of supine position
- Intraoperative time of onset and duration of significant changes in the SSEP amplitude and latency
- Any changes in surgical protocol as a result of reported SSEP changes (i.e. reposition of arms or head).
- Status of SSEPs at the end of the surgery

Postoperative day 1:

- Study team members will see patients on postoperative day 1 to complete a questionnaire (see attached form)

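### The study aims to find potential causes of SSEP changes, but position is the only intraoperative exposure recorded, so non-positional changes cannot be reliably told apart from positional ones

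*Combined protocol and SAP*

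**What the plan says.** The purpose, under Aims, is to "determine the incidence and potential causes of significant changes in SSEP waveforms" and to relate those changes to the neurological state of the brachial plexus after surgery.

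The Data collection section lists three intraoperative exposures:
- how the limbs and head are placed: "Patient positioning intraoperatively (hand, arm, and head position"
- when the steep or leg-raised posture is adopted: "Intraoperative time of positioning in extreme Trendelenburg and or lithotomy position"
- when that posture is given up, which appears as "Intraoperative time of resumption of supine position"

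Three further intraoperative items describe the SSEP change or the response to it. One covers when it began and how long it lasted, given as "Intraoperative time of onset and duration of significant changes in the SSEP amplitude and latency". Another covers what the team did about it, with repositioning as the only example: "Any changes in surgical protocol as a result of reported SSEP changes (i.e. reposition of arms or head". The third is whether the signals had recovered when surgery ended. The patient-level items are age, sex, weight and height, and "Medical history (hypertension, diabetes mellitus, history of smoking". A questionnaire follows on postoperative day 1.

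Under Methods, the device "alerts the user to check the waveform view for artifact or potential limb positioning effect". It also pauses averaging during cautery interference, lets the clinician enter time-stamped comments, and produces a report with space for interpretation. EPAD Setup adds a Train of Four recording and an alert threshold of a 50% amplitude fall and/or a 10% latency rise against a baseline set at the start of the case.

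The Data Analysis Plan has two elements: descriptive statistics for demographics, and a correlation between reported weakness or numbness and EPAD values. The target accrual is 40, and the Power Statement reads N/A.

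**The concern.** A study of causes must record the candidate causes, at the time they could act. Here the only exposure followed through the case is position. The protocol itself names a non-positional explanation for an alert, namely artifact, but does not list the clinician's judgement on it as study data.

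Three results rest on the same set of changes: how often they occur, what is associated with them, and how they relate to symptoms the next day. If artifact or other non-positional changes cannot be separated out:
- incidence may be too high as a measure of threatened nerves;
- position may be credited with changes it did not produce;
- the symptom correlation may be pulled toward zero by changes that have nothing to do with nerve injury.

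**Working it through.** The plan gives no figure to reproduce. The check sets the aim, the variables and the analysis side by side.

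**Step 1. Classify the listed items.** Apart from the day 1 questionnaire, Data collection has eight items.

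| Type | Items | Count |
|---|---|---|
| Intraoperative exposure, positional | limb and head position; Trendelenburg/lithotomy time; return to supine | 3 |
| Intraoperative exposure, non-positional | none | 0 |
| The SSEP change or the response to it | onset and duration; changes made in response; end-of-surgery status | 3 |
| Patient factors, fixed for the case | demographics; medical history | 2 |

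The fixed factors may mark who is susceptible. They cannot explain why a change began at one moment rather than another.

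**Step 2. Look for non-positional sources in the documents.** Methods names artifact as one of two explanations for an alert. The alert threshold in EPAD Setup is defined by amplitude and latency alone and is not specific to cause. Cautery suspension deals with high-frequency interference only, and the user is still told to check for artifact. The comments and Train of Four exist on the device but are absent from Data collection.

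**Step 3. Ask whether the recorded times can separate the causes.** They can in part. A change that starts just after a recorded move, or that resolves after repositioning or return to supine, is more plausibly positional. But the baseline is set at the start of the case. Whatever alters the waveform during the period in the surgical position overlaps with that position. Timing does not separate two explanations that are present together.

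**Step 4. Look for a rule or an analysis.** No section gives a rule for assigning a cause, and the Data Analysis Plan contains no analysis of causes.

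**Step 5. Illustration of size, on assumed inputs.** Let s be the share of all changes that are non-positional and q the fraction of monitored time spent in the surgical position. Suppose non-positional changes fall at random over monitored time, and all positional changes occur in position. The non-positional share of changes seen in position is then s·q / (s·q + 1 − s).

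| s | q = 0.7 | q = 0.9 |
|---|---|---|
| 0.1 | 0.07/0.97 = 7% | 0.09/0.99 = 9% |
| 0.3 | 0.21/0.91 = 23% | 0.27/0.97 = 28% |
| 0.5 | 0.35/0.85 = 41% | 0.45/0.95 = 47% |

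The documents give neither s nor q, and the result stays close to the s put in. The table shows only that looking within the in-position period removes few of the non-positional changes. It does not estimate the error in this study, and it equals a misattribution rate only if every in-position change is put down to position.

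**The case against.** A reader might infer that every non-positional change will be attributed to position by default, or that position is the only candidate cause in the dataset. The documents support neither. There is no attribution rule and no planned analysis of causes, so a change could simply be left unexplained. The position items are several distinct exposures, and patient-level factors are collected as well. Onset, duration, repositioning, return to supine and end-of-surgery status give some evidence for or against a positional cause.

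The other arguments on that side are these:
- **Artifact is partly handled.** The device sends the user to inspect the waveform and pauses for cautery, and its report has room for interpretation. A significant change as recorded need not mean a raw alert, and the analysis section does not say that artifact enters the correlation. This is fair, but nothing says artifact is removed or how that would be recorded.
- **Physiological causes are not in the documents.** No section says blood pressure, temperature or anaesthetic agent alters SSEPs. This is correct, and the point does not need it: the protocol's own reference to artifact is enough.
- **The omission may be recoverable.** The medical record number is kept internally, and the HIPAA section notes that identifiers allow later additions from the record. That helps for anaesthesia-record fields. It helps less for the artifact judgement, because entering device comments is optional.

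These arguments limit the conclusion to a risk of misattribution. They do not supply the missing variables.

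**Conclusion.** The point holds in a limited form. With the listed variables, non-positional intraoperative changes cannot be reliably distinguished from positional ones. The stated aim of finding potential causes is therefore only partly answerable, and misattribution to position is a risk, not a certainty.

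Inflated incidence and a diluted symptom correlation are possible consequences. They rest on two assumptions: that some artifact or other non-positional changes are kept among the significant changes, and that these are unrelated to postoperative symptoms. The size cannot be derived from the documents, and the illustrative shares above should not be used to judge severity. The change is worth making because it bears on a stated aim and costs little.

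**What to change.** **Data collection.** For each significant change, and at baseline in the same patient, record:
- the artifact or not-artifact judgement, as a required field (for the baseline, of the baseline trace);
- the EPAD Train of Four and any event comments;
- blood pressure, temperature, and anaesthetic agent and concentration, abstracted from the anaesthesia record. These are candidate non-positional factors, and it is assumed that the record holds them.

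**Data Analysis Plan.** Pre-specify a rule that classes each change as position-related, artifact, other/systemic or undetermined. Position-related could require, for example, onset after a recorded position change and/or reversal after recorded repositioning or return to supine. State the criteria for the other classes too. Classification should be done without knowledge of the day 1 questionnaire. Report incidence by class. Run the symptom correlation on non-artifact changes and, alongside it, on all changes, so that the effect of exclusion is visible.

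**Alternative.** If these data will not be collected, narrow the aim to associations between position and SSEP changes.

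**Cost.** A few more fields for up to 40 patients, taken from the EPAD report and the anaesthesia record, with no new procedure and no change to patient care. Some changes will be undetermined, and splitting them into four classes will leave small cells, so results by class should be read as descriptive.

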#### **Resources:**

Equipment and pads are readily available in clinical practice as part of standard of care.

#### **Subject Information**

Target accrual: 40

Subject population (children, adults, groups): adults, 18 years or older

Inclusion Criteria:

- Patients scheduled to undergo robotic assisted laparoscopic genitourinary surgery
- Patients who are scheduled to have EPAD monitoring as part of their clinical care intraoperatively.

Exclusion Criteria:

- Patients with previous history of polyneuropathy, carpal tunnel, ulnar neuropathy, or similar neurological deficiencies

#### **Research Activity**

Check all that apply and complete the appropriate sections as instructed.

1. **Drug & Device:** Drugs for which an investigational new drug application is not required. Device for which (i) an investigational device exemption application is not required; or the medical device is cleared/approved for marketing and being used in accordance with its cleared/approved labeling. (Specify in the Methods section)
2. **Data** (medical record, images, or specimens): Research involving use of existing and/or prospectively collected data.

## HIPAA Identifiers and Protected Health Information (PHI)

Protected health information is medical data that can be linked to the subject directly or through a combination of indirect identifiers.

Recording identifiers (including a code) during the conduct of the study allows you to return to the medical record or data source to delete duplicate subjects, check a missing or questionable entry, add new data points, etc. De-identified data is medical information that has been stripped of all HIPAA identifiers so that it cannot be linked back to the subject. De-identified data is **rarely** used in the conduct of a research study involving a chart review.

**Review the list of subject identifiers below and, if applicable, check the box next to each HIPAA identifier being recorded at the time of data collection or abstraction.** Identifiers apply to any subject enrolled in the study including Mayo Clinic staff, patients and their relatives and household members.

**Internal** refers to the subject's identifier that will be recorded at Mayo Clinic by the study staff.

**External** refers to the subject's identifier that will be shared outside of Mayo Clinic.

Check all that apply:	INTERNAL	EXTERNAL
Name		
Mayo Clinic medical record or patient registration number, lab accession, specimen or radiologic image number	x	
Subject ID, subject code or any other person-specific unique identifying number, characteristic or code that can link the subject to their medical data	x	
Dates: All elements of dates [month, day, and year] directly related to an individual, their birth date, date of death, date of diagnosis, etc.		
Note: Recording a year only is not a unique identifier.		
Social Security number		
Medical device identifiers and serial numbers		
Biometric identifiers, including finger and voice prints, full face photographic images and any comparable images		
Web Universal Resource Locators (URLs), Internet Protocol (IP) address numbers, email address		
Street address, city, county, precinct, zip code, and their equivalent geocodes		
Phone or fax numbers		
Account, member, certificate or professional license numbers, health beneficiary numbers		
Vehicle identifiers and serial numbers, including license plate numbers		
Check 'None' when none of the identifiers listed above will be recorded, maintained, or shared during the conduct of this study. (exempt category 4)	 None	 None

**Power Statement:**

N/A

**Data Analysis Plan:**

Descriptive statistics will be used to present information about study participants' demographics. Correlation analysis will be performed to calculate correlation between reported incidence of residual weakness or numbness and values obtained by EPAD monitoring system.

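### The only planned outcome analysis is an unspecified correlation, whose size depends on the symptom rate and the form of the EPAD variable as well as on how well EPAD separates patients

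*Combined protocol and SAP*

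**What the plan says.** The stated purpose has two parts: to find the incidence and potential causes of significant SSEP changes, and to "correlate these changes with neurologic status of the brachial plexus after robotic surgery". The Data Analysis Plan has two sentences. The first covers baseline description: "Descriptive statistics will be used to present information about study participants' demographics". The second is the only outcome analysis: "Correlation analysis will be performed to calculate correlation between reported incidence of residual weakness or numbness and values obtained by EPAD monitoring system". It names no coefficient, no specific EPAD variable, no confidence interval, and no measure of discrimination such as an AUC, sensitivity or specificity.

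Subject Information gives "Target accrual: 40", and the Power Statement is marked not applicable.

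The documents allow at least two readings of the EPAD side of the correlation:

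- **A measured quantity.** Data collection lists "Intraoperative time of onset and duration of significant changes in the SSEP amplitude and latency".
- **A yes/no alert.** EPAD Setup gives the rule for it: "A decrease of 50% in amplitude and/or an increase of 10% of the latency of one of the potentials as compared to baseline will trigger".

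The outcome comes from a visit the next day: "Study team members will see patients on postoperative day 1 to complete a questionnaire (see attached form". That form is not in the text available for review.

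**The concern.** A correlation coefficient is usually read on a scale where 1 means a perfect relation. When one variable is yes/no and the other is continuous with few ties, that reading fails. Even if every symptomatic patient has a worse EPAD value than every asymptomatic patient, the coefficient falls short of 1, and for rank correlations the shortfall grows as symptoms become rarer. The same discriminating ability also gives different coefficients at different symptom rates.

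The coefficient is the plan's only answer to the second part of the purpose. With no sample-size rationale, readers will rely on the estimate itself. They could take a monitor that ranked patients correctly to be weakly related to outcome. They also could not compare the result with a series that has a different symptom rate.

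**Working it through.** **Plan's own figure.** There is none to reproduce: 40 is given without inputs.

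**Inputs.** n = 40 (Subject Information). The outcome is taken as yes/no, the natural reading of a reported incidence. The number symptomatic, k, is an assumption varied from 1 to 20, with p = k/40.

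**Step 1. Perfect separation, EPAD value continuous.**

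- Spearman without ties: the mean ranks differ by n/2 and the rank variance is (n² − 1)/12, so the coefficient is √(3p(1−p)) × n/√(n² − 1). At k = 2: √(3 × 0.05 × 0.95) = 0.3775, times 1.0003, is 0.38.
- Pearson, all 40 values together normal: for large n it is φ(z)/√(p(1−p)), where z is the upper-p normal quantile. At k = 2: 0.1031/0.2179 = 0.47. Simulation at n = 40 gives a mean of 0.46.
- Pearson, all 40 values together lognormal (right-skewed): simulation mean.

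| Symptomatic of 40 | Spearman, no ties | Pearson, normal (n = 40) | Pearson, lognormal | AUC |
|---|---|---|---|---|
| 1 | 0.27 | 0.35 | 0.64 | 1.00 |
| 2 | 0.38 | 0.46 | 0.74 | 1.00 |
| 4 | 0.52 | 0.575 | 0.79 | 1.00 |
| 8 | 0.69 | 0.70 | 0.78 | 1.00 |
| 20 | 0.87 | 0.80 | 0.61 | 1.00 |

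Every row describes the same perfect ranking. At k = 2 the reported figure could be 0.38 or 0.74, depending on the coefficient and the shape of the values.

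**Step 2. Fixed, imperfect discrimination.** This uses a different model: normal values with equal variance within each group. For AUC 0.85, d = √2 × z(0.85) = 1.414 × 1.036 = 1.466, and r = d√(pq)/√(1 + d²pq), with q = 1 − p.

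- k = 2: pq = 0.0475, d²pq = 0.102, r = √(0.102/1.102) = 0.30
- k = 4: pq = 0.09, r = 0.40
- k = 8: pq = 0.16, r = 0.51
- k = 20: pq = 0.25, r = 0.59

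The coefficient nearly doubles with no change in discrimination.

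**Step 3. Other forms of the EPAD variable.**

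- An alert present in exactly the symptomatic patients gives phi = 1.00 at any rate.
- If alerts include every symptomatic patient but are twice as common as symptoms, phi = √(p(1−a)/(a(1−p))), with a the alert rate. At k = 2: √(0.05 × 0.90/(0.10 × 0.95)) = 0.69. This is no longer perfect separation.
- If duration of change is scored zero when there is no change (an assumption) and is nonzero only in symptomatic patients, Spearman is 1.00, 1.00 and 0.99 at k = 2, 4 and 8.
- If the symptomatic group is shifted by 6 within-group SD, the mean Pearson coefficient is 0.80 at k = 2 and 0.88 at k = 4.

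**Step 4. The test.** Under untied perfect separation the Spearman p-value is 0.09 at k = 1, 0.016 at k = 2 and 0.0006 at k = 4. The exact two-sided rank-sum p-value is 2/C(40, k): 2/40 = 0.05, 2/780 = 0.003 and 2/91,390 = 0.00002.

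**The case against.** The strongest reply is that low coefficients are not inevitable. Four stronger readings are tempting, and the documents support none of them.

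- **That the symptom rate alone caps the coefficient.** This is true of untied rank correlations but not of Pearson. The formula in Step 2 tends to 1 as d grows at any symptom rate, and the lognormal and shifted-group results are well above the normal-value figures.
- **That a perfect monitor would be reported as weakly related.** The plan fixes neither the coefficient nor the variable. Tied durations or a matching alert, both obtainable from what the protocol records, can give values at or near 1. The plan also sets out no scale of weak, moderate and strong. The supportable word is could.
- **That symptoms will be uncommon.** No rate is given; the Methods say only "Patients scheduled for genitourinary surgery are often at risk for developing nerve injuries due to intraoperative positioning". At 8 of 40 the perfect-separation values are already about 0.70. A graded questionnaire score cannot be excluded either.
- **That the study would miss the association.** Step 4 shows that a small coefficient can still have a small p-value. The issue is the size of the reported effect.

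It can also be said that this is a descriptive study, that incidence and causes come first in its purpose, and that an AUC from 2 to 4 cases is imprecise. All of that is fair and keeps the point modest. It does not rescue the coefficient: a figure that changes with the symptom rate, the coefficient and the data shape for the same ranking is a poor summary of separation. The correlation is just as imprecise with few cases, but shows it less.

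**Conclusion.** The point stands in a limited form. If 1 to 4 of 40 patients are symptomatic and the EPAD value is continuous with few ties, perfect separation could appear as 0.27 to 0.52 (Spearman) or about 0.35 to 0.575 (Pearson, roughly normal values). An AUC of 0.85 could appear as anything from 0.30 to 0.59 as cases go from 2 to 20. These figures rest on an assumed symptom rate, a yes/no outcome and the stated distributions; other forms of the EPAD variable give much higher values. What is at stake is the interpretation and comparability of the result, not the validity of the study or, in general, its significance test. The change should be made because it is cheap and the plan currently leaves the measure open.

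**What to change.** Amend the second sentence of the Data Analysis Plan as follows.

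1. Name the EPAD variable or variables, with one value per patient and the direction that counts as worse.
2. For a continuous or ordered EPAD value, make the main association measure the AUC with a 95% confidence interval and an exact Wilcoxon rank-sum test. Use an interval method that does not collapse to zero width when separation is complete.
3. For the alert defined in EPAD Setup, report sensitivity and specificity against the symptom with exact 95% intervals and the two-by-two counts.
4. Show each symptomatic patient's EPAD value against the distribution in the others.
5. Treat any correlation coefficient as secondary, name it, and do not label it weak, moderate or strong.
6. State what is reported if no patient is symptomatic. At a 5% rate this has probability 0.95⁴⁰ = 13%, and at 2.5% it is 36%. Neither a correlation nor an AUC is then defined.

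The cost is a few sentences, with no new data or patients. The downside is visible imprecision. For example, if the alert occurs in all symptomatic patients, the exact lower limit for sensitivity is 0.025^(1/k), which is 0.16 with 2 cases and 0.40 with 4.
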